Study Center(s)	Multi-center; 10 sites total
Number of Subjects	60
Diagnosis and Main Inclusion Criteria	History of chronic oral food refusal and be primarily fed through a G or G-J tube
Study Product, Dose, Route, Regimen	Megestrol will be dosed at 6 mg/kg/d at weeks 10-11, at 4 mg/kg/d at week 12, at 2 mg/kg/d at week 13, and fully tapered at the end of week 13.
Duration of administration	4 weeks of Megestrol, 24 weeks of iKanEat behavioral intervention
Reference therapy	Placebo for Megestrol
Statistical Methodology	The outcome measure for Aim 1 is a binary variable indicating whether a child obtains 90% or more caloric intake on oral feeding at the end of the intervention. A chi-square test or Fisher's exact test will be used to compare the rates of oral feeding between the two groups.

CONFIDENTIAL

This material is strictly confidential and is intended solely for the guidance of clinical investigation. Do not disclose or use except as authorized in writing by the study sponsor

1 Introduction

This document is a protocol for a human research study. This study is to be conducted according to US and international standards of Good Clinical Practice (FDA Title 21 part 312 and International Conference on Harmonization guidelines), applicable government regulations and Institutional research policies and procedures.

Feeding problems requiring medical intervention occur in 3-10% of children (1). Premature infants are overrepresented among children with feeding problems (2). Improved preterm infant survival has increased the prevalence of feeding problems in older infants and toddlers (3). In addition, severe feeding problems occur in 40-70% of children with chronic medical conditions (4,5). Neonates with long intensive care hospitalizations may lose opportunities for learning to eat and may associate eating with pain or discomfort (6). Gastrostomy (G-) and gastrojejunal (G-J) tube feeding requirements may persist for months or years resulting in chronic oral food refusal. As the prevalence of gastrostomy tube feeding has increased, so have the challenges associated with managing a child with tube feeding and transitioning a child from tube to oral feeding (7,8). Previous research on transitioning children from tube to oral feeding indicates that most programs are inpatient or intensive day treatment, and many children are not successful (8).

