Our team developed a novel interdisciplinary outpatient protocol for transitioning children from tube to oral feeding (9,10) called iKanEat. Data indicate iKanEat is effective for transitioning tube fed children to eating by mouth. iKanEat results in statistically significant and clinically meaningful increases in oral eating. iKanEat is composed of several key components, including two medications – amitriptyline and megestrol. However, our most recent work (HD066629)(11) demonstrated that amitriptyline is not a necessary component of the protocol, as all children who completed the protocol consumed 100% of their calories orally at post treatment regardless of receiving amitriptyline or placebo. The current proposal is a randomized controlled trial of the second medication (megestrol) compared to placebo, to ensure that the addition of a 4-week course of megestrol improves child outcomes within the iKanEat protocol. Because corticosteroids can have significant side effects, it is critical we determine if the benefits of megestrol as part of iKanEat outweigh the risks of the medication.

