
During the iKanEat protocol, we expect the child to lose weight during weeks 10-14 as the children taper off the tube. We inform parents of this expected weight loss and monitor the children closely. Despite this, in the previous trial there were instances of parents withdrawing their children during this weight loss period despite the physician guidance that the weight loss was expected and safe. It is critical that we learn more about this stressful period of the iKanEat protocol so we can better help parents through this transition. The current study design will allow us to learn more about how and when parent stress changes throughout the protocol in order to target supplemental treatment efforts related to parent stress.

Quality of Life.

Our most recent study (HD066629) also examined the role of pain and quality of life in tube weaning. Findings demonstrate improvement in pain symptoms ($t = 1.85$, $p = .006$) and in several areas of quality of life (i.e., growth and development, $t = -2.285$, $p < .05$; behavior, $t = -2.376$, $p < .05$; general health perceptions, $t = -2.232$, $p < .05$; parental impact: emotional and time, $t = -3.718$, $p < .005$) in the transition from tube to oral feeding.(11) In the current protocol we will assess whether successful transition to oral feeding has an effect on parent and child quality of life.

Remote Interventions.

CONFIDENTIAL

This material is strictly confidential and is intended solely for the guidance of clinical investigation. Do not disclose or use except as authorized in writing by the study sponsor

Our team has extensive experience delivering multidisciplinary feeding team clinical visits via interactive televideo. These visits are delivered as part of routine feeding team care in our clinic, and include both new patient visits and return patient visits. This clinical experience will serve our team well regarding the current scope of work.

Gut Microbiota

The gut microbiota refers to the species of bacteria living in the gut, and plays an essential role in digestive and immune function. Little is known about the effect formula feeding has on the microbiome, and the effects of transitioning from tube feeds to oral feeding. In the current protocol, we will assess whether successful transition to oral feeding has an effect on the gut microbiota.

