4.3 Subject Recruitment and Screening

Sixty subjects are needed for our analysis plan, so with a maximum of 20% drop out (which exceeds drop out from our previous work), a total sample of 72 will need to be recruited over the 5 year project (for more information see Sample Size Determination in Data Analysis Plan section). To allow for study start up and completion phases, we will need to recruit approximately 20 subjects per year when in active recruitment. Currently, the University of Kansas Medical Center team sees 12 new patients per month, Children's Mercy Hospital sees 12 new patients per month, University of California San Diego/Rady Children's Hospital sees 8 new patients per month, the New Orleans site sees 8 new patients per month, Arnold Palmer Hospital for Children sees 8 new patients per month, and Children's Hospital of Philadelphia sees 12 new patients per month, resulting in a total potential recruitment base of 60 feeding subjects per month across our primary sites. Based upon clinic data, 20% of the patients seen will meet inclusion/exclusion criteria (resulting in 12/month or 144/year). Of these, we predict that half will be given permission to participate, given the highly medically complex nature of many children with feeding problems (resulting in 72/year). Assuming that half of eligible families participate (36/year), current clinic volume at participating sites will result in successfully meeting recruitment goals.

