To address Aim 1, analyses will be conducted using Generalized Linear Mixed Models with a logit link within SAS Proc GLIMMIX to model the binary outcome of transitioned to oral feeding (y/n) defined as at least 90 percent of calories consumed orally. Fixed effects (dummy variables) will be entered for each site as described by McNeish and Stapleton (2016) to account for the clustering of the participants within sites. This will result in essentially, a logistic regression model with appropriate standard errors. Sex, age at initiation, treatment condition, and interactions with treatment condition will enable us to examine the effect of group assignment on successful transition to oral feeding by week 24. Interactions between treatment group and sex will be examined but will not be sufficiently powered to reach definitive conclusions about sex differences. In addition to overall effects, subgroup analyses will be reported for males and females to examine treatment effects within sex groups.

To address Aim 2, we will determine whether any of our participants in either group have adrenal sufficiency levels outside of the normal range at any time point. Should any participant have levels outside of the normal range, we will descriptively examine the individual characteristics associated with this, including group assignment, medical diagnoses, sex, and age at initiation. These characteristics will be reported descriptively.

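### The Aim 1 model has no rule for a missing week 24 outcome and the primary population can exclude withdrawn children, which costs power and leaves bias of unknown direction

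*Combined protocol and SAP*

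**What the plan says.** Section 7.1 (Planned Analyses, Aim 1) specifies a logistic mixed model, fitted in SAS, whose purpose is "to model the binary outcome of transitioned to oral feeding (y/n"), where success means taking 90% or more of calories by mouth. Site dummies, sex, age, treatment and interactions with treatment enter the model, in order to "examine the effect of group assignment on successful transition to oral feeding by week 24". The Study Summary names a different test for the same outcome: a chi-square or Fisher's exact test "will be used to compare the rates of oral feeding between the two groups". Neither place says how a child without a week 24 recall is handled. No imputation, scoring rule or sensitivity analysis for missing outcomes appears anywhere in the documents.

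Other parts of the plan bear on this:

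- **Section 4.3:** "Sixty subjects are needed for our analysis plan, so with a maximum of 20% drop out", 72 are to be recruited.
- **Population(s) for Analysis (end of section 7):** the primary analysis is in a protocol-compliant population, meaning children with the intended drug exposure and procedures. The all-treated analysis is secondary. An all-randomized set is defined but given no analysis.
- **Section 4.4.2:** families who withdraw are asked to continue assessments, including the diet recall, so that the primary endpoint is still available.
- **Section 3.3, item 12:** some failed weans are expected to stay in the study and report tube feeding.
- **Sections 1 and 1.3:** in the earlier trial "all children who completed the protocol consumed 100% of their calories orally at post treatment regardless of receiving amitriptyline or placebo", and "in the previous trial there were instances of parents withdrawing their children during this weight loss period".

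**The concern.** A logistic model with one record per child leaves out any child with no response value. Without a stated rule, complete-case analysis is what the plan delivers, and the sample-size reasoning expects it.

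That would matter little if loss were unrelated to outcome. The plan's own history suggests otherwise. If everyone who completed the earlier trial succeeded, a child who did not succeed was among the non-completers, and some families left in the phase when weaning is hardest. Restricting the analysis to children with an observed outcome, or to protocol-compliant children, then selects on something close to the outcome.

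At stake are the power of the primary test, whether the model can be fitted at all if few failures remain, and an estimate that can move either way if loss differs by arm.

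**Working it through.** **Inputs.** From section 7.1: megestrol success 0.90, odds ratio 0.21 (placebo odds over megestrol odds), N = 72, power 0.80. From section 5.3: 1:1 allocation, so 36 per arm. From section 4.3: at most 20% dropout. Assumed, because the documents do not give them: two-sided 5% significance and the share of failures lost in each arm.

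**Design rates.** Megestrol odds are 0.90/0.10 = 9. Placebo odds are 9 × 0.21 = 1.89, so the placebo rate is 1.89/2.89 = 0.654. The true difference is 0.246.

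**The plan's own power figure.** Power = Φ{[|p1 − p2| − 1.96·√(p̄(1−p̄)(1/n1+1/n2))] / √(p1(1−p1)/n1 + p2(1−p2)/n2)}. With p̄ = 0.777 and n1 = n2 = 36 this is Φ{(0.2460 − 0.1923)/0.0937} = Φ(0.573) = 0.72. The stated value is 0.80; the same formula one-sided gives 0.82. The significance level is not stated, so the mismatch is a separate point. I use 0.72 as the baseline.

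**Observed rates after loss.** With success p, and with shares mS of successes and mF of failures missing, the observed rate is p(1−mS) / [p(1−mS) + (1−p)(1−mF)]. If only failures are lost (mS = 0), the observed odds ratio is 0.21 × (1 − mF megestrol)/(1 − mF placebo).

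| Failures lost, megestrol / placebo | Overall loss | Observed rates | Difference | Odds ratio | Power |
|---|---|---|---|---|---|
| none | 0% | 0.900 v 0.654 | 0.246 | 0.21 | 0.72 |
| 50% / 50% | 11% | 0.947 v 0.791 | 0.157 | 0.21 | 0.47 |
| 90% / 90% | 20% | 0.989 v 0.950 | 0.039 | 0.21 | 0.16 |
| 100% / 100% | 22% | 1.00 v 1.00 | 0 | not estimable | – |

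For the 90% row, overall loss is (0.10 × 0.9 + 0.346 × 0.9)/2 = (0.090 + 0.311)/2 = 0.20, the planned maximum.

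**Failures left to model in the 90% row.** Megestrol: 36 × 0.10 × 0.10 = 0.36. Placebo: 36 × 0.346 × 0.10 = 1.25. About 1.6 expected failures would have to support treatment, sex, age, interactions and dummies for up to ten sites, so separation is likely. The normal approximation is stretched here, and 0.16 is indicative only.

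**Loss that differs by arm.**

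- 50% of megestrol and 80% of placebo failures lost: 0.21 × 0.50/0.20 = 0.525, toward no effect. Overall loss is (0.050 + 0.277)/2 = 16%.
- The reverse: 0.21 × 0.20/0.50 = 0.084, away from no effect. Overall loss is (0.080 + 0.173)/2 = 13%.
- The reverse pattern with no true effect (0.75 in both arms, assumed): 0.938 v 0.857, odds ratio 1 × 0.20/0.50 = 0.40, spuriously favouring megestrol.

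All three patterns lie within the 20% allowance.

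**Missing counted as not transitioned, all 36 per arm.** If only failures are lost, rates stay at 0.900 v 0.654, odds ratio 0.21, power 0.72. If 20% are lost regardless of outcome, rates become 0.90 × 0.8 = 0.72 and 0.654 × 0.8 = 0.523, odds ratio 0.43, power 0.40. Complete cases then have power 0.62 (28.8 per arm).

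**The case against.** Four points can fairly be made for the plan.

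1. **Withdrawal is not the same as a missing outcome.** Section 4.4.2 plans a recall after withdrawal, pursued by phone, email and certified letter. This is a real mitigation. It ends if a family refuses, section 4.3 still budgets for up to 20% loss, and the protocol-compliant population can exclude the child after the recall has been obtained.
2. **Failure can be observed.** Section 3.3 item 12 expects failed weans under follow-up, and the Aim 3 power text assumes 60% or 70% success across groups. A reader might infer that missing outcomes are mostly failed weans. The documents do not support that. Section 1.3 reports instances of withdrawal without a count. Randomization is at week 0 while drug and tube taper start around week 10, so earlier losses cannot be failed weans. Other removals follow serious adverse events (section 6.11), cortisol results (section 3.4) or missed doses (section 5.3).
3. **The odds ratio is robust to one kind of loss.** A reader might infer that the comparison is biased toward no difference. For the planned logit model this is not established: loss that depends on outcome alone leaves the odds ratio at 0.21 until no failures remain. The difference in rates, which the Study Summary test compares, does shrink. With arm-specific loss the odds ratio moves either way, and the safety removals above make such loss plausible.
4. **Scoring missing as failure is not neutral.** When loss is unrelated to outcome it dilutes the effect and loses more power than complete cases do. This stands and has to be priced into the fix.

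These points limit the claim about direction and extent. They do not supply the missing rule.

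**Conclusion.** The concern holds in this form. The primary analysis has no rule for a missing week 24 outcome, defaults to complete cases, and sits in a population that can discard outcomes the protocol works to collect. Withdrawal is a likely but not exclusive route to failure. The consequences are loss of power, possible separation and bias whose direction cannot be known in advance.

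In the worst case computed within the planned 20% loss, power falls from 0.72 to 0.16 with an unbiased odds ratio. With unequal loss the odds ratio ranges from 0.084 to 0.525 around a true 0.21. These figures rest on the design rates, two-sided 5% and assumed loss shares. The documents give no data on how failures and successes are lost by arm, so the figures show what the plan permits and do not forecast what will happen.

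**What to change.** Before unblinding, amend section 7.1 and the populations paragraph as follows:

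- Make the all-randomized population primary for Aim 1, with the protocol-compliant and all-treated analyses supportive.
- Use every week 24 recall obtained, including those after withdrawal.
- Count a child with no week 24 recall as not transitioned, unless a tube-feeding report or follow-up contact documents status at week 24. The report is sent only while a child is tube fed, so its absence should not be read as success.
- Add multiple imputation and a tipping-point analysis, both with assumptions that may differ by arm.
- Tabulate missing outcomes by arm, timing and reason.

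The cost is mainly wording and some programming; no new data collection is needed. The statistical cost is dilution if loss is unrelated to outcome: at 20% loss, power is 0.40 against 0.62 for complete cases. The detectable odds ratios in section 7.1 must therefore be restated under the new rule.

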1.3 Review of Literature

Feeding

Our team has published several studies of pediatric feeding difficulties. Our early work examined the relationship between feeding difficulties and medical complexity (27), and found that by the time of introduction of solid food, preterm children more often demonstrated difficulty than full-term children. Also, medical factors, primarily the need for breathing assistance, accounted for more of the variance in this relationship than prematurity alone. We have also assessed parent perceptions of mealtime behaviors in children who are tube fed, and learned that parents report surprisingly high levels of stress around the mealtime, both for themselves and their children (28). We have also examined pediatric sensory processing issues related to feeding problems (29) and found that 67% of children who present for treatment have sensory profile scores in the abnormal range. Also, co-occurring diagnoses are frequent in the areas of developmental, gastrointestinal, and neurological areas. This foundational work led to the multidisciplinary protocol which we call iKanEat that was designed to move these complicated children to oral eating on an outpatient basis.

Clinical Data: iKanEat

In 2008, our team published a retrospective chart review of the first 9 patients to undergo our iKanEat tube weaning protocol clinically (30). At that time, the protocol included two medications (amitriptyline and megestrol) as well as behavioral and oral motor/sensory components. Results from this initial retrospective study indicated that the nine initial patients were 100% orally fed at the end of the intervention period, and 8 of the 9 were 100% orally fed six months later (one patient with cerebral palsy had stamina issues and was only able to sustain 50% of intake orally over the long term). This pilot work led us to NIH funding to conduct a randomized controlled trial of amitriptyline, one of the two medications in the protocol (HD066629). The findings (11) suggest that 100% of children who completed the protocol moved from tube feeding to total oral feeding, regardless of group assignment (amitriptyline, placebo). More specifically, of the children who completed the 6 month protocol, % kilocalories/day obtained orally (our primary outcome measure) increased statistically significantly from $M = 31.51\%$ ($SD = 16.09\%$) to 100%. Therefore, it does not appear that amitriptyline is a necessary component of the iKanEat protocol.

Parent Stress

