7.1 Sample Size Determination and Statistical Methods

For Aim1 (To assess the efficacy of megestrol as part of the 24 week iKanEat protocol), if at least 90% of the treatment group successfully transitions (in pilot 100% successfully transitioned), with 72 participants, we would have .80 power to detect an odds ratio of .21. With 60 participants, we would have power to detect an odds ratio of .18. If only 75% of the treatment group successfully transitions, we will still have .80 power to detect an odds ratio of .25 with our smallest expected sample size of 60.

For Aim 2 (To assess the safety of megestrol as part of the 24 week iKanEat protocol), all analyses are descriptive, so a power analysis is not conducted.

For Aim 3 (To examine the effect of the transition from tube to oral feeding on parent stress and parent and child quality of life), with 60 participants, we would have .78 power to detect differences in slopes over the four data points equivalent to a standardized effect size of $d=.75$ or larger. With a sample size of 72, there will be .80 power to detect a difference in slopes equivalent to a standardized effect size of .70. To answer those questions in which the grouping factor is success in treatment, such as 3A (The transition to oral feeding will temporarily increase parent stress at week 14 at the cessation of tube feeding, with a return to baseline by week 24) and 3B (The transition to oral feeding will increase parent/child quality of life at 24 weeks compared to week 0), assuming that 60% of the participants across groups are successful, we would have sufficient power to detect effects equivalent to a standardized effect size of $d=.42$ or larger. With a sample size of 60, the minimum detectable effect size would increase to $d=.59$. If 70% percent are successful, with 72 participants we can detect effects equivalent to $d=.61$, and with 60 participants $d=.70$. These are moderate sized effects.

Planned Analyses

CONFIDENTIAL

This material is strictly confidential and is intended solely for the guidance of clinical investigation. Do not disclose or use except as authorized in writing by the study sponsor

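### The Aim 1 logistic model has no rule for an empty failure cell: if no megestrol child fails, overall or within one sex, that treatment effect has no finite estimate and its Wald test cannot reject

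*Combined protocol and SAP*

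**What the plan says.** The Planned Analyses part of Section 7.1 uses GLIMMIX with a logit link "to model the binary outcome of transitioned to oral feeding (y/n) defined as at least 90 percent of calories consumed orally". On clustering it says "Fixed effects (dummy variables) will be entered for each site"; the Study Summary gives "Multi-center; 10 sites total". The covariates follow: "Sex, age at initiation, treatment condition, and interactions with treatment condition will enable us to examine the effect of group assignment". The result is described in these terms: "This will result in essentially, a logistic regression model with appropriate standard errors". Section 7.1 adds that the sex interaction will not be powered for firm conclusions, but also that "subgroup analyses will be reported for males and females to examine treatment effects within sex groups".

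On expected success, Section 7.1 plans for "at least 90% of the treatment group successfully transitions (in pilot 100% successfully transitioned" and gives 75% as a second case. Section 1.3 reports 9 of 9 children fully orally fed at the end of treatment in a chart review and, for the earlier randomised trial, "100% of children who completed the protocol moved from tube feeding to total oral feeding". The Population(s) for Analysis paragraph makes the protocol-compliant set primary.

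No section says what happens if a cell is empty or the fit does not converge. No penalised, exact or profile-likelihood method is named. The Study Summary names a chi-square or Fisher's exact test for the same outcome, without saying whether that test or the model is primary.

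**The concern.** A logistic model fitted by maximum likelihood needs both successes and failures in each group whose effect it estimates. If the megestrol group has no failures, the likelihood keeps rising as the treatment coefficient grows. The software stops at an arbitrary large value with a far larger standard error, and the Wald statistic falls towards zero. The same happens within a sex once treatment-by-sex is in the model or the sexes are analysed separately.

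This is the direction in which the trial hopes to go. A clear benefit could be reported as not significant, or as an infinite odds ratio, and any rescue analysis would be chosen after the data were seen.

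**Working it through.** **Inputs.** Arms of 30 and 30 (Section 3.1), or 36 and 36 if all 72 recruits are analysed (Section 4.3). Allocation 1:1 within site (Section 5.3). Megestrol success 90% or 75%, with detectable odds ratios .21 (N=72, 90%), .18 (N=60, 90%) and .25 (N=60, 75%) at power .80 (Section 7.1). Assumed, because not stated: 5% significance level and sidedness, equal site sizes, an even sex split (15 megestrol children per sex) and no true site effect.

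**1. The plan's own figures.** Placebo odds = megestrol odds × odds ratio.
- 90%, .21: 9 × .21 = 1.89, so 1.89/2.89 = 65.4%.
- 90%, .18: 9 × .18 = 1.62, so 1.62/2.62 = 61.8%.
- 75%, .25: 3 × .25 = 0.75, so 0.75/1.75 = 42.9%.

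Exact enumeration of the two-arm Wald test gives power .804, .794 and .815 at one-sided 5%, so the stated .80 is reproduced on that basis. At two-sided 5% the same test gives .698, .676 and .728. The rest of this check uses two-sided 5%.

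**2. Chance of an empty cell.** With success rate p, no failures among 30 has probability p^30. At least one sex with no failures among 15 has probability 2p^15 − p^30.

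| p | No failures overall | At least one sex without failures |
|---|---|---|
| 75% | 0.02% | 2 × .0134 − .0002 = 2.7% |
| 90% | 4.2% | 2 × .2059 − .0424 = 37% |
| 95% | 21% | 2 × .4633 − .2146 = 71% |

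**3. What the test does at the boundary.** Failures of 0/30 v 10/30 have Fisher p = .0008, yet the maximum-likelihood odds ratio is infinite and the Wald test cannot reject. With one or two failures the test works:
- 1/30 v 8/30: odds ratio (29/1)/(22/8) = 10.5, standard error √(1 + 1/29 + 1/8 + 1/22) = 1.098, z = 2.15, p = .032.
- 2/30 v 9/30: odds ratio (28/2)/(21/9) = 6.0, standard error .833, z = 2.15, p = .032.

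**4. Exact two-arm power, 30 per arm, placebo 61.8%, two-sided 5%.**

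| Megestrol success | Wald | Fisher | Likelihood ratio |
|---|---|---|---|
| 85% | .50 | .43 | .57 |
| 90% | .68 | .65 | .78 |
| 95% | .69 | .86 | .94 |
| 98% | .43 | .95 | .99 |
| 100% | 0 | .99 | 1.00 |

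Wald power rises until about 90–95% success and then falls. The other two tests keep rising.

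**5. Adjusted model by simulation** (N=60, 10 sites of 6, sex, age; ranges are across repeated runs).

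| Megestrol v placebo | Model | Wald | Firth penalised likelihood ratio |
|---|---|---|---|
| 90% v 61.8% | main effects | about .71 | about .72 |
| 95% v 61.8% | main effects | .64–.69 | .88–.91 |
| 100% v 61.8% | main effects | 0 | .99 |
| 75% v 42.9% | main effects | .76–.77 | .69–.72 |
| 90% v 61.8% | with interactions | .33–.40 | .66–.70 |
| 95% v 61.8% | with interactions | .20–.22 | .87–.88 |
| 75% v 42.9% | with interactions | about .70 | about .70 |

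In the interaction rows treatment is tested at average sex and age. Without site dummies the main-effects comparison at 95% is about .68 v .90, so the site terms are not the cause.

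**The case against.** Several points on the other side are sound.

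- **Few failures are not enough.** A reader might infer that the model breaks down whenever failures are rare. Step 3 shows otherwise: one or two failures normally leave the main-effects estimate finite, and it can be significant. Only an empty cell causes the problem.
- **The pilot does not predict 100%.** The figure rests on 9 of 9 (exact lower 95% limit .025^(1/9) = 66%) and on completers only in the earlier trial. Section 1.3 says some parents withdrew children from that trial, and Section 7.1 powers at 90% and 75%. The protocol-compliant primary set makes high success plausible, no more.
- **It is not generally true that the better megestrol works, the less the model can show it.** That describes Wald inference above about 95% success, or earlier once interactions are in. At 90% with main effects there is no loss, and at 75% Firth gains nothing.
- **The Wald test is inferred.** Section 7.1 names a model and software, not a test. A likelihood-ratio test of the same fit also avoids the power loss, though its type I error in this setting has not been checked here.
- **Interaction results depend on coding.** With 0/1 sex and uncentred age, the treatment coefficient at 90% has power of only .06 (Wald) or .13 (Firth), because it then tests a different effect. Firth's method alone does not settle which effect is tested.
- **Fisher's test is named in the Study Summary** and tolerates an empty cell. One therefore cannot assume that the primary analysis would come out non-significant.

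The last point reduces the problem without removing it. No section makes Fisher's test primary or a fallback, and it does not supply the adjusted or within-sex estimates that Section 7.1 promises. Turning to it after seeing separation would be a post-hoc choice.

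**Conclusion.** The concern holds as a gap in the plan that should be fixed. As written, the Section 7.1 model gives no usable treatment inference when no megestrol child fails, and none for the affected contrast when no megestrol child of one sex fails.

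At the plan's 90% assumption the overall case is uncommon (4%), but the within-sex case is not (37%). Including the interactions then costs the Wald test about 30 percentage points of power against Firth's method. At 95% the main-effects loss is about 20 points or more. At 75% there is no gain, and Firth's power is a little lower with main effects.

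These figures assume two-sided 5%, placebo success of 61.8% (42.9% for the 75% case), 10 equal sites, an even sex split and the default GLIMMIX tests. The documents do not support saying that the model fails across the whole range the plan expects.

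**What to change.** Before unblinding, amend Section 7.1 as follows.

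1. Test the overall Aim 1 treatment effect in a main-effects model (site, sex, age, treatment) fitted by Firth penalised likelihood (PROC LOGISTIC with the FIRTH option), using the penalised likelihood-ratio test and profile interval.
2. Fit the treatment interactions in a separate model with sex and age centred, and use the same method for the within-sex estimates.
3. Report the risk difference with a score-type 95% interval, which stays defined at 100% success.
4. State whether the Study Summary test or the Section 7.1 model is primary, with the significance level and sidedness.

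The cost is SAP wording and a small program change. The odds ratio is shrunk slightly towards 1, and power may be slightly lower if success rates are well below 90%.
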